8.2 Dose Modifications for Futibatinib

8.21 Dose Modifications for Futibatinib for Expected Adverse Events

CTCAE System/Organ/Class (SOC)	ADVERSE EVENT	ACTION**
Blood and lymphatic system disorders	Anemia Grade 3	Omit dose until resolved to \leq Grade 1 or baseline • If resolved \leq 7 days, then maintain dose level • If resolved $>$ 7 days, then reduce 1 dose level
	Grade 4	Omit dose until resolved to \leq Grade 1 or baseline
Blood and lymphatic system disorders	Febrile neutropenia	Omit dose until resolved, then reduce 1 dose level
Eye disorders	Eye disorders - Other, specify - retinal pigment epithelial detachment (RPED)	Continue at current dose and continue periodic ophthalmic evaluation: • If resolved \leq 14 days to \leq Grade 1, then maintain dose level • If resolved $>$ 14 days to \leq Grade 1, then omit dose until resolved, then resume at same dose level or a lower dose
Gastrointestinal disorders	Diarrhea Grade 2	Omit futibatinib dose until resolved to \leq Grade 1 or baseline
	Grade 3	Omit dose until further evaluation and cause is determined If resolved within 21 days, and deemed related to futibatinib, then reduce 1 dose level
Gastrointestinal disorders	Mucositis oral Grade 3	If AE persists despite optimal supportive care: Omit futibatinib dose until resolved to \leq Grade 1 or baseline
Gastrointestinal disorders	Nausea Grade 3	If AE persists despite optimal supportive care (See Section 9.0): Omit futibatinib dose until resolved to \leq Grade 1 or baseline
Gastrointestinal disorders	Vomiting Grade 3	If AE persists despite optimal supportive care (See Section 9.0): Omit futibatinib dose until resolved to \leq Grade 1 or baseline
Investigations	Alanine aminotransferase increased >5 x ULN AND Aspartate aminotransferase increased >5 x ULN AND Blood bilirubin increased ≥ 3 x ULN	Omit futibatinib for up to 14 days until resolved to \leq Grade 1 or baseline, then restart at same dose level If related to futibatinib then reduce 1 dose level
Investigations	For ALT >20 x ULN, and AST >20 x ULN, or Blood bilirubin increased >10 x ULN	Permanently discontinue futibatinib

CTCAE System/Organ/Class (SOC)	ADVERSE EVENT	ACTION**
Investigations	Hyperphosphatemia Grade 3 Serum phosphorus level >7 - ≤10 mg/dL	Dose reduce futibatinib to the next lower dose level and initiate or intensify phosphate lowering therapy (See Section 9.0 for management suggestions) Re-assess serum phosphate within 7 days and at least once a week. If the serum phosphorus level has resolved to ≤Grade 2 within 14 days after dose reduction, continue futibatinib at the reduced dose level. If the serum phosphorus level has not resolved to ≤Grade 2 after 14 days, further reduce futibatinib from the last reduced dose level (or no lower than 12 mg QD). If the serum phosphorus level has not resolved to ≤Grade 2 after 14 days of the second dose reduction of futibatinib (or no lower than 12 mg QD), omit dosing with futibatinib until it is resolved to ≤Grade 2 before resuming futibatinib at the reduced dose prior to dose interruption.
Investigations	Hyperphosphatemia Grade 4 Serum phosphate >10 mg/dL	Omit futibatinib until it is resolved to ≤Grade 2, then resume futibatinib at the next lower dose level and intensify phosphate lowering therapy Re-assess serum phosphate within 7 days and at least once a week If after 2 dose interruptions and 2 dose reductions the serum phosphorus level has not resolved to ≤Grade 2 after 14 days, permanently discontinue futibatinib
Investigations	Neutrophil count decreased Grade 4	Omit dose until resolved to ≤Grade 2 or baseline • If resolved ≤7 days, then maintain dose level • If resolved >7 days, then reduce 1 dose level
Investigations	Platelet count decreased Grade 3	Omit dose until resolved to ≤Grade 1 or baseline • If resolved ≤7 days, then maintain dose level • If resolved >7 days, then reduce 1 dose level
	Grade 4	Omit dose until resolved to ≤Grade 1 or baseline, then reduce 1 dose level
Skin and subcutaneous tissue disorders	Palmar-plantar erythrodysesthesia syndrome Grade 3	Omit dose until resolved to ≤Grade 1 or baseline • If resolved ≤21 days, then maintain dose level • If resolved >21 days, then reduce 1 dose level
	Rash, maculopapular	Omit dose until resolved to ≤Grade 1 or baseline • If resolved ≤21 days, then maintain dose level • If resolved >21 days, then reduce 1 dose level
All others not specified above and at least possibly related to futibatinib	Grade 3	Omit dose until resolved to ≤Grade 1 or baseline Reduce by 1 dose level from the previous level
	Grade 4 (nonlab)	Discontinue futibatinib

CTCAE System/Organ/Class (SOC)	ADVERSE EVENT	ACTION**
	Grade 4 lab abnormalities	Omit dose until resolved to \leq Grade 1 or baseline Futibatinib will be permanently discontinued if assessed by the Investigator as life threatening. If it is in the best interest of the patient to continue treatment in the opinion of the Investigator and after discussion with the Sponsor, the patient can continue treatment at a reduced dose level

** Use the following to describe actions in the Action column:

- **Omit** = The current dose(s) for the specified drug(s) during a cycle is skipped. The patient does not make up the omitted dose(s) at a later time.
- **Hold/Delay** = The current dose(s) of all drugs during a cycle is delayed. The patient does make up the delayed dose(s) when the patient meets the protocol criteria to restart drugs.
- **Discontinue** = The specified drug(s) are totally stopped.

NOTE: Interrupt futibatinib if any adverse events are intolerable, regardless of the grade (including Grade 1 and 2). If or when the adverse event resolves to a tolerable state, consideration can be given to resuming futibatinib at the same dose if deemed appropriate or reduced by one dose level if needed

NOTE: If the patient experiences a significant adverse event requiring a dose reduction at the start of the next cycle, then the dose will remain lowered for that entire subsequent cycle. If that cycle is completed with no further adverse events $>$ Grade 2, then the dose may be increased, at the investigator's discretion, one level at a time, in the following cycles.

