7.11 Treatment medication table – Cycles 1-9

Agent	Dose Level	Route	Day	ReRx
futibatinib	20 mg*	oral	Once daily on Days 1-21	Q3w
pembrolizumab	200 mg	IV	1	Q3w

Cycle length = 21 days ± 3 days

*Investigator may start patients at lower dose (16mg) if clinically indicated (e.g., patient history of diarrhea) after discussion with PI

Once patients have completed Cycle 9, the cycle length can be increased to 6 weeks with imaging every other cycle (~12 weeks).

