8.0 Dosage Modification Based on Adverse Events

Strictly follow the modifications in this table for the first **two** cycles, until individual treatment tolerance can be ascertained. Thereafter, these modifications should be regarded as guidelines to manage mild-to-moderate, but not debilitating, side effects. If multiple adverse events are seen, administer dose based on greatest reduction required for any single adverse event observed.

Reductions or increases apply to treatment given in the preceding cycle and are based on adverse events observed since the prior dose.

Special Considerations

- The treating investigator may reduce/withhold/discontinue a patient's dose for an AE of any grade/duration where s/he believes it to be in the best interests of the patient.
- In patients who have met the criteria for permanent discontinuation, resumption of futibatinib may be considered if the patient is deriving clinical benefit and has fully recovered from the related event after consulting with PI.
- Any consideration to modification of the above dose modification guidelines should be discussed with the Principal Investigator for approval or disapproval in advance.

→ ***ALERT: ADR reporting may be required for some adverse events (See Section 10.0)*** ←

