9.6 Ocular Toxicity

9.61 Retinal Pigment Epithelial Detachment (RPED)

Futibatinib can cause RPED, which may cause symptoms such as blurred vision. Median time to first onset of RPED is generally 40days.

Perform a comprehensive ophthalmological examination, including OCT of the macula,prior to initiation of therapy, every 2 months for the first 6 months, and every 3 months thereafter. For onset of visual symptoms, refer patients for ophthalmologic evaluation urgently, with follow-up every 3 weeks until resolution or discontinuation of futibatinib.

Withhold or reduce the dose of futibatinib if not resolved to \leq Grade 1 within 14 days of symptom onset.

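### The RPED row in Section 8.21 ties dose omission to an event that has already resolved, which is inconsistent with Section 9.61; footnote 10 of the test schedule also leaves out the macular OCT

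*Combined protocol and SAP*

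**What the plan says.** **Dose rule in Section 8.21.** The RPED row carries no grade limit. Its lead instruction is "Continue at current dose and continue periodic ophthalmic evaluation". Two branches follow. If the event resolves to Grade 1 or lower in 14 days or less, the dose level is kept. If resolution to Grade 1 or lower took more than 14 days, "then omit dose until resolved, then resume at same dose level or a lower dose". The notes to the table define omission: "The current dose(s) for the specified drug(s) during a cycle is skipped", and the skipped dose is not made up.

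**Dose rule in Section 9.61.** "Withhold or reduce the dose of futibatinib if not resolved to" Grade 1 or lower within 14 days, counted from the onset of symptoms.

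**Status of the table.** Section 8.0 says "Strictly follow the modifications in this table for the first" two cycles, and treats the modifications as guidelines after that. The same section lets the treating investigator reduce, withhold or discontinue a patient's "dose for an AE of any grade/duration" when that is in the patient's best interests. A note under 8.21 calls for interruption when any adverse event is intolerable, whatever its grade.

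**Eye examinations.** Section 9.61 requires a comprehensive examination that includes macular OCT before therapy, every 2 months for the first 6 months, and every 3 months thereafter. Footnote 10 of the Section 4.1 test schedule sets the same on-treatment intervals and lists the mandatory content: external examination, slit lamp, and dilated fundoscopy. It does not name OCT. It accepts a baseline examination up to 6 months old.

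**The concern.** RPED is a named futibatinib toxicity with its own dose rule. The rule appears in two places, and they should tell a site the same thing about the case that matters most: an event that has not settled by day 14. As the 8.21 row is worded, a coordinator or pharmacist working from the table finds no branch for that case and falls back on the lead instruction to keep dosing. Section 9.61 tells the same person to withhold or reduce.

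The OCT omission is a separate and simpler point. A site that orders eye examinations from the test schedule could complete everything footnote 10 lists and still lack the imaging that 9.61 requires, including the baseline image against which later findings would be compared.

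What is at stake is consistent handling of an ocular toxicity, not the trial's statistical properties.

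**Working it through.** No power, error-rate or sample-size figure is involved. The check is a comparison of the texts.

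**1. Apply the 8.21 row literally.** Let t be the time the event takes to resolve to Grade 1 or lower.

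- t of 14 days or less: the first branch applies, and the dose is kept.
- At day 14 with the event still present: neither branch is met, because both are conditioned on the event having resolved. The lead instruction to continue is all that is left.
- t greater than 14 days, once resolution has occurred: the second branch now applies and says to omit until resolved. The event has already resolved, so the period of omission has length zero.

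On this reading the row never interrupts dosing for an unresolved event.

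**2. Apply 9.61 to the same patient.** At day 14 from symptom onset with the event above Grade 1, futibatinib is withheld or reduced. The two sections differ for exactly this patient.

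**3. Check whether this is just the table's usual style.** It is not.

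- The same form of words is sound in rows that stop the drug first. The Grade 3 palmar-plantar erythrodysesthesia row omits dosing at once and then says "If resolved >21 days, then reduce 1 dose level". There the time to resolution decides the dose at restart, which is coherent.
- The Grade 3 hyperphosphatemia row reduces the dose but keeps the patient on drug. Its next step is triggered by phosphorus *not* having come down to Grade 2 or lower after 14 days, and Section 9.5 gives the same rule.
- The RPED row keeps the patient on drug, as the hyperphosphatemia row does, but borrows the wording of the rows that omit first.

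**4. Apply 8.21 as it was probably meant.** If the second branch is read as covering an event not resolved by 14 days, the trigger matches 9.61. Two differences remain:

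- Action: 8.21 gives only omission; 9.61 also allows reduction without interruption.
- Clock: 9.61 counts from symptom onset; 8.21 gives no start. Neither section provides a start for an RPED found without symptoms at a scheduled examination.

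**5. Compare the examination content.** On-treatment intervals agree between 9.61 and footnote 10. Content differs by one item, OCT, which appears in 9.61 and nowhere else in the supplied text. Under 9.61 the examinations that must include OCT in the first 6 months are baseline plus months 2, 4 and 6: 1 + 3 = 4. That is the number of examinations the omission touches, not a count of OCTs that would be missed. Because footnote 10 accepts a baseline examination up to 6 months old and does not ask for OCT, an earlier examination without OCT satisfies the footnote and leaves 9.61 unmet.

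**The case against.** The best defence is that the literal reading defeats itself. An instruction to omit until resolved presupposes an event that is still present, so a sensible clinician reads the branch as covering an event not resolved by 14 days. On that reading the threshold equals 9.61's, and omitting satisfies both sections. Section 8.0 supplies the missing option to reduce, because the investigator may reduce or withhold for an event of any grade or duration, in any cycle. Footnote 10 states a minimum and does not exclude OCT, while 9.61 requires OCT in plain terms. Section 6.9b also has an ophthalmologist confirm that each patient is suitable.

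Most of this stands, and it limits the weight of the point. It does not remove it. A dose table should not need repair by its reader, and discretion to stop is not the same as 9.61's direction to withhold or reduce.

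A reader might go further and infer either of two stronger things. The documents support neither.

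- *That the two sections give contrary orders.* They share the 14-day, Grade 1 threshold, and the 8.21 branch plainly has an unresolved event in view. This is faulty wording that leaves a gap, not a different policy.
- *That the table's strict status in the first two cycles forces continued dosing in a sizeable share of patients.* The investigator's discretion is in the same Section 8.0 and is not confined to later cycles. The documents give no RPED incidence and no distribution of onset beyond a median of about 40 days. With "Cycle length = 21 days ± 3 days", two cycles last at most 2 × 24 = 48 days, so the first scheduled on-treatment eye examination, at 2 months, comes after the strict period. Events found before then would come to light mainly through visual symptoms, for which 9.61 calls for urgent referral.

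**Conclusion.** The second branch of the RPED row in 8.21 is wrong as written and should be corrected. Read literally, it leaves an event unresolved at day 14 under continued dosing, which is inconsistent with 9.61. Read as probably intended, it still lacks 9.61's option to reduce and a start for the clock. The omission of macular OCT from footnote 10 is real, but it is an omission and not a contradiction.

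The size is one branch of one table row and one missing item in one footnote. The conclusion rests only on the wording of Sections 8.0, 8.21, 9.61 and footnote 10. No patient count, excess exposure or number of missed OCTs is claimed, because the documents give nothing from which to derive one. No effect is claimed on PFS at 6 months, on the secondary endpoints, or on the adverse event summary in Section 16.6.3.

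**What to change.** (a) Reword the second branch of the 8.21 RPED row along these lines: *If not resolved to Grade 1 or lower within 14 days of symptom onset (or of first detection if asymptomatic), withhold until resolved and then resume at the same or a lower dose, or reduce.* Use the same action and the same clock in 9.61, so that an RPED found without symptoms also has a start date.

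(b) Add *OCT of the macula* to the list of mandatory examination content in footnote 10 of the test schedule.

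The cost is wording in one table row, one sentence of 9.61 and one footnote. Section 9.61 already requires OCT on this schedule, so no procedure or visit is added.

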8.1 Dose Levels (Based on Adverse Events in Tables 8.2 and 8.3)

Dose Level	Futibatinib (TAS-120)	Pembrolizumab Cycles 1-9	Pembrolizumab Cycles 10+
1 *	20 mg	200 mg q3w	400mg q6w
-1	16 mg	--	--
-2	12 mg	--	--

*Dose level 1 refers to the starting dose.

Patients may be started at dose -1 if clinically indicated after discussion with PI

NOTE: If either of futibatinib or pembrolizumab is discontinued, the patient can continue on the other drug, unless specified otherwise in the dose modification tables. If both are discontinued, the patient will go to survival follow-up (Section 4.2).

→ → ***Use the NCI Common Terminology Criteria for Adverse Events (CTCAE) current version 5.0* unless otherwise specified*** ← ←

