8.3 Dosage Modifications for Pembrolizumab

There are no dose reductions for pembrolizumab.

Holding and discontinuation of pembrolizumab should follow clinical practice and most current product information.

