9.4 Diarrhea/Colitis

All events of diarrhea or colitis should be thoroughly evaluated for more common etiologies other than immune-induced effects.

NOTE: Futibatinib can cause non-immune-related diarrhea which can be managed clinically.

- For events of significant duration or severity or associated with signs of systemic inflammation or acute-phase reactants, check for immune-related colitis.

9.41 Grade 1- without abdominal pain/or blood in stool and symptoms.

Infectious etiologies should be ruled out. Discontinue medications that may exacerbate colitis (e.g., NSAIDS) while investigating etiology. Patients may be managed symptomatically (e.g., loperamide). Instruct patients to report any increase in stools.

9.42 Grade 2- without abdominal pain/or blood in stool and symptoms <1 week, and resolve to Grade 0 or 1. Continue to monitor. Infectious etiologies should be ruled out. Discontinue medications that may exacerbate colitis (e.g., NSAIDS) while investigating etiology. Patients may be managed symptomatically (e.g., loperamide). Instruct patients to report any increase in stools.**9.43 Grade 2- with symptoms >1 week despite optimal supportive care, consider steroid therapy –first choice is budesonide at 12 mg once daily (if unable to obtain budesonide and/or patient continues to have diarrhea after 72 hours of use start systemic steroids at 0.5 mg/kg/day prednisone or equivalent- can be given in two doses- especially for patients that have nocturnal diarrhea).**

** Infectious etiologies should be ruled out. Discontinue medications that may exacerbate colitis (e.g., NSAIDS) while investigating etiology.

9.44 Grade 3 or greater- despite optimal supportive care including loperamide, and with other etiologies ruled out consider systemic steroids at 1-2 mg/kg/day prednisone or equivalent (may be given in two daily doses- especially for patients that have nocturnal diarrhea).

** Assess for dehydration. Patients may require hospitalization for IV

steroids (1-2 mg/kg/day methylprednisolone). Discontinue medications that may exacerbate colitis (e.g., NSAIDS) while investigating etiology.

** Once patients have improvement of symptoms to Grade 0 or 1 taper of steroids should occur over at least 1 month. If patients have been started on budesonide in addition to systemic steroids, start tapering the prednisone FIRST.

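### The Grade 3 diarrhea row of table 8.21 ends futibatinib omission when a cause is found and names no recovery grade, although the Grade 2 row above it requires recovery

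*Combined protocol and SAP*

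**What the plan says.** Section 8.21 sets the futibatinib dose modifications.

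- **Grade 2 diarrhea:** "Omit futibatinib dose until resolved to" Grade 1 or lower, or baseline. Attribution plays no part.
- **Grade 3 diarrhea:** "Omit dose until further evaluation and cause is determined". One further sentence follows: "If resolved within 21 days, and deemed related to futibatinib, then reduce 1 dose level".

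Section 8.0 makes the table binding for the first two cycles and a guideline after that. The same section lets the treating investigator withhold drug for an adverse event of any grade or duration.

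**The concern.** The more severe grade carries the looser stated condition for ending omission. Grade 2 diarrhea must recover before futibatinib resumes. For Grade 3, the stated endpoint is that the cause has been worked out.

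The case that matters is Grade 3 diarrhea attributed to something other than futibatinib, such as immune colitis or infection. That attribution is a realistic decision in this trial. Section 15.17 lists diarrhea among the most common events (15% or more) in all three futibatinib studies, and Section 15.27 lists it as very common (10% or more) for pembrolizumab.

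Section 9.4 notes that "Futibatinib can cause non-immune-related diarrhea which can be managed clinically". Restarting futibatinib during active Grade 3 diarrhea of another cause could therefore add a second cause. Section 7.51 shows how seriously the protocol takes prolonged Grade 3 diarrhea: more than 3 days despite optimal supportive care counts as excessive toxicity. That rule covers only the first six patients and events at least possibly related to study medication, so it serves here only as a marker of severity.

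**Working it through.** The protocol gives no figure to reproduce. The check is a reading of the row, a count of the table, and a search for a restart grade elsewhere.

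**1. What the Grade 3 diarrhea row covers, read literally**

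- Related to futibatinib and resolved within 21 days: reduce one dose level.
- Related and not resolved by 21 days: no instruction.
- Not related to futibatinib: only the first sentence applies. Its condition is met once the cause is named, at whatever grade the diarrhea then is.
- No cause found: the first sentence's condition is never met, even if the diarrhea has gone.

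The third line is the gap at issue. It narrows once the patient improves to Grade 2, because the Grade 2 row then requires Grade 1 or lower, or baseline. What remains is the period while diarrhea is still Grade 3.

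**2. How the other rows end omission**

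Table 8.21 has 21 rows. Two only discontinue futibatinib (the extreme ALT/AST/bilirubin row and the non-laboratory Grade 4 catch-all). That leaves 21 − 2 = 19 rows that omit it:

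| Omission ends on | Rows | Number |
|---|---|---|
| Grade 1 or lower, or baseline | Anemia G3 and G4; diarrhea G2; mucositis, nausea and vomiting G3; ALT/AST/bilirubin; platelets G3 and G4; hand-foot G3; rash; catch-all G3; catch-all G4 laboratory | 13 |
| Grade 2 or lower (neutrophils: or baseline) | Phosphate G3 and G4; neutrophils G4 | 3 |
| Resolved, no restart grade given | Febrile neutropenia; retinal pigment epithelial detachment | 2 |
| Cause determined | Diarrhea G3 | 1 |

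13 + 3 + 2 + 1 = 19, and 19 − 1 = 18 end on some form of resolution.

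Two of the 19 set the dose by relatedness within the row: Grade 3 diarrhea and ALT/AST/bilirubin. The latter names recovery to Grade 1 or lower, or baseline, and then says "then restart at same dose level If related to futibatinib then reduce 1 dose level". It is an imperfect comparator, because it also limits the omission to at most 14 days.

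**3. Whether other text supplies the restart grade**

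- *Catch-all rows of 8.21:* they cover "All others not specified above and at least possibly related to futibatinib". Grade 3 diarrhea is specified above, and the case at issue is unrelated to futibatinib. Each exclusion is enough alone.
- *Section 8.1 note:* if one drug is discontinued, "the patient can continue on the other drug, unless specified otherwise in the dose modification tables". This points back to the table.
- *Section 8.3:* "Holding and discontinuation of pembrolizumab should follow clinical practice and most current product information". It does not govern futibatinib.
- *Section 9.4:* covers work-up, loperamide, steroids and consultation. Its Grade 0 or 1 criterion is for starting the steroid taper.
- *Section 9.8:* refers pembrolizumab-related events to clinical standard of care and gives no futibatinib restart grade.
- *Definition of omission under 8.21:* skipped doses are not made up. It adds no restart condition.
- *Section 8.0 discretion and the intolerable-event note under 8.21:* the first is permissive. The second ties resumption to the event becoming tolerable. Neither names a grade.

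**4. How long the table binds**

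2 cycles × 21 days = about 42 days.

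**The case against.** The strongest answer is that the row never says futibatinib may resume once a cause is named. Its only instruction after omission begins from resolution within 21 days, so the authors probably expected resolution first. A sensible clinician would also read the Grade 3 row as adding a work-up and a dose reduction to the Grade 2 requirement, not as relaxing it. This stands as to intent. A reader might infer that the protocol authorizes dosing through Grade 3 diarrhea, and the documents do not support that. The restart is implied by where the stated condition ends, and the row is silent on unrelated events. But no text says that the Grade 2 recovery requirement carries over to Grade 3, and the literal condition is the one a site is told to follow strictly in the first two cycles.

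The second answer is that practice would prevent harm. Investigator discretion, the intolerable-event note, the Section 9.4 work-up and standard care under Section 9.8 all stand between this wording and a patient. That is right, and it limits the importance of the point. It does not supply the missing grade.

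The third answer is that other rows are imperfect too. The ALT/AST/bilirubin row has its 14-day limit, and the retinal detachment row is awkwardly worded. So the 18-to-1 count shows a drafting inconsistency and should not be read as a measure of risk.

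**Conclusion.** The point holds as a minor safety wording correction. The Grade 3 diarrhea row is the only one of 19 whose omission ends on something other than resolution, and it is less strict on restart than the Grade 2 row. The gap is confined to diarrhea still at Grade 3 with a cause judged not to be futibatinib. It matters most in the first two cycles, when the table is binding.

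The conclusion rests on a literal reading of the row and on no other section giving a futibatinib restart grade. The documents give no rate for this situation, so no number of affected patients is claimed. Sample size, error rates and the efficacy analysis are unaffected.

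A reader might also infer that the dose should be reduced whenever futibatinib cannot be excluded as a cause. The documents do not support that as part of this correction: the present row reduces only when the event is deemed related, and the defect is the missing recovery condition.

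**What to change.** Replace the first sentence of the Grade 3 diarrhea row with: *Omit dose and evaluate for cause; do not resume until resolved to Grade 1 or lower, or baseline.* Keep the second sentence in substance: "If resolved within 21 days, and deemed related to futibatinib, then reduce 1 dose level". Add no mandatory reduction when relatedness cannot be excluded. Leave the restart dose in unrelated or undetermined cases to the investigator.

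The evaluation for cause stays, since the choice of treatment depends on it. Diarrhea that resolves without a cause being found can then restart, which the present sentence does not literally allow. The dose for related diarrhea that resolves only after 21 days remains unspecified; the team may settle that separately.

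The cost is one table row in the next amendment and a slightly longer futibatinib interruption in some patients, mainly those with immune or infectious diarrhea. Only patients still to be dosed under the table would benefit.
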